 - For school-based research where class time is used, describe in detail the activities planned for non-subjects and explain where both subjects and non-subjects will be located during the research activities.
 - Indicate that the instruments used are in the public domain or provide appropriate documentation of permission to use each scale.
 - Use any diagrams, charts or tables necessary to make subject participation clear to readers. Attach additional pages if necessary.

Protocol Title: Assessing an HIV Education and Screening Intervention in African American Churches

Protocol Type: Expedited/Full Board Application

Date Submitted: 11/21/2017

Approval Period: 12/05/2017-12/04/2018

Important Note: This Print View may not reflect all comments and contingencies for approval. Please check the comments section of the online protocol. Questions that appear to not have been answered may not have been required for this submission. Please see the system application for more details.

- Be sure to identify what procedures are experimental and what are standard of care or established practice for the condition/situation.

Please note: Do NOT respond "See Attachment Section". If you would like to add tables, charts, etc., attach those files in the Attachment section (#16).

Determination of Number of Churches/Sample Size: Power Analysis. Sample size calculations were based on: a) change in expected self-reported HIV testing rates (primary outcome) from baseline to 12-month assessment and b) a group randomization and matched pair design based on a range of 5 to 7 paired churches (10 to 14 churches). To calculate power, we used Hayes' approach for cluster randomized trials through the specification of a coefficient of variation (CV) of cluster rates, which defines relative variation between clusters, rather than an intraclass correlation. We used our TIPS pilot study findings as the basis of our analysis (there are no other known studies on pre-post HIV testing rates with AA participants nested in churches) and expect similar HIV testing rates in the proposed study. Based on our CV estimates, we would have sufficient power with 10 to 12 churches (110 baseline participants per church; >65 participants at 12 months) to achieve 84% to 91% power, respectively, to detect this difference with a Type I error rate of 5%; these power calculations are conservative. However, we will include 14 churches to protect power against possible church attrition.

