Data collection. Data collection for this study consists of recruited Wave 1 participants completing a Health Beliefs and Behaviors survey assessment at baseline, 6 months, and 12 months. Wave 2 participants will complete the survey four times: baseline 1, baseline 2 (6 months), 12 months, and 18th months. The Health Beliefs and Behaviors survey instrument (see Attachment) was developed by the research team led by [name] and tested for reliability/validity in the TIPS pilot study. The survey inquires

Protocol Title: Assessing an HIV Education and Screening Intervention in African American Churches

Protocol Type: Expedited/Full Board Application

Date Submitted: 11/21/2017

Approval Period: 12/05/2017-12/04/2018

Important Note: This Print View may not reflect all comments and contingencies for approval. Please check the comments section of the online protocol. Questions that appear to not have been answered may not have been required for this submission. Please see the system application for more details.

participants about history of HIV/STD screening, facilitators/barriers to HIV screening, beliefs/social norms related to screening, risky behaviors associated with HIV/STDs, and exposure/satisfaction with study activities. Data collection procedures use the survey follow below.

1. Each participating church pastor will introduce the study PI (or research study coordinators) during the designated church service (e.g., Sunday morning or midweek service) and church community outreach event, which will be determined by each participating church's pastor and leadership. The study PI (or research study coordinator) will then review the scripted consent form information (See Appendix A) during the church service with church members and during the church outreach event with community members.
2. After the church services and church community outreach events, the research team will then review the informed consent script (See Appendix A) with willing adult members in the church's fellowship hall or large meeting room. The informed consent script will be used as a screening tool to identify eligible participants.

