At least 2 church leaders, or church health liaisons, will coordinate implementation of their church's TIPS activities. These CHLs will be trained to monitor and report their church's implementation activities monthly over the 12-month study period by responding to questions on the CHL Intervention or Comparison Church Implementation Monitoring Form (Independent on if they're in an intervention and comparison church; see Attachments). CHL's will complete implementation questions (no personal or behavioral information is requested) directly into REDCap, an online data entry database supported by UMKC's Center for Health Insights, which has been used extensively by research and community organizations around the world (see Section 11.c for further information about REDCap). CHL's at participating churches will have password access to this system to enter process data on intervention implementation information (e.g., number of persons attending events, location of events, organizations and resources assisting in implementing events, challenges and accomplishments related to the events). No personal health or behavioral data will be collected on intervention Implementation -- only program

Protocol Title: Assessing an HIV Education and Screening Intervention in African American Churches

Protocol Type: Expedited/Full Board Application

Date Submitted: 11/21/2017

Approval Period: 12/05/2017-12/04/2018

Important Note: This Print View may not reflect all comments and contingencies for approval. Please check the comments section of the online protocol. Questions that appear to not have been answered may not have been required for this submission. Please see the system application for more details.

evaluation information. The online system will significantly reduce the amount of time needed for church liaisons to provide implementation data by allowing them to select responses from a pull down menu and provide short string text for open ended responses.

Research Design: We will use a 2-arm, research design with 14 churches (7 intervention and 7 standard information control churches) matched on church membership size, SES, and denomination. Matched churches will be randomly assigned to one of two Waves and then to intervention or standard information arms within their Wave. To optimize study management, 8 churches will be in Wave 1, and 6 Wave 2 churches will be 6-month waitlisted.

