Important Note: This Print View may not reflect all comments and contingencies for approval. Please check the comments section of the online protocol. Questions that appear to not have been answered may not have been required for this submission. Please see the system application for more details.

i) **Describe the statistical methods of the research and plans for analysis of the data (i.e. planned statistics, justification of sample size, etc.).**

Data will be initially summarized using means, standard deviations, and percentages. Our primary outcome is self-reported receipt of HIV/STD testing (tested vs. not-tested) at 12 months. We'll also examine outcomes at 6 months. Churches are the unit of randomization and participants nested in churches will be the level of analysis. Therefore, differences between intervention and standard information groups will be analyzed using random effects logistic regression to account for the clusters and the pairing, or matching, of churches. Multilevel, multivariate models will include fixed-effect terms for experimental condition and potential mediators and moderators, as well as random effect terms for church nested in treatment condition and individual nested within church. This approach has been widely used in other church-based studies. Adjusted odds ratios for HIV testing (and confidence intervals) will be computed for mediators/moderators. Other covariates will be added as indicated by univariate analyses conducted on baseline data. A propensity score matched analysis will also be run using all available covariates.

Amendment for post study focus group survey/discussion:

Survey data will be summarized using means, standard deviations, and percentages. Focus group discussions will be audio-recorded, transcribed, and coded. Coding protocols will include initial transcription "open-coding" (e.g., identifying key words, themes, behavioral descriptions), category grouping (e.g., church-based health screening barriers), and code map development to further categorize and retrieve factors (e.g., challenges, facilitators) related to delivery/receipt of programming/services and intervention refinement strategies/tools. Intercoder agreement will be assessed with the kappa coefficient.

* * * Drugs and Devices * * *

5. Drugs and Devices

Device

Will the study be registered on an online website?

Y

If yes, state which website(s):

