Only six of the eight churches that met the eligibility criteria participated in Wave 1. Palestine Missionary Baptist Church will not be participating due to other church priorities. Victorious Life Church was delayed due to other commitments and will participate in Wave 2. Therefore, Wave 2 churches will include 8 churches.

Church recruitment is ongoing for Wave 2 and additional churches will be added in subsequent amendments.

March 2016 Amendment:
Added participating churches
- Paseo Baptist Church
- Swope Parkway United Christian Church

August 2016 Amendment
~ Removed church name, El Shaddai International Ministries Church, previously listed under "March 2016 Amendment".
~ Added participating church, Good Samaritan Baptist Church

Amendment for focus groups survey/discussion: Recruitment of post study survey/focus group participants will take place in participating churches by the PI (or other research team member), who will attend participating churches' services/ministry meetings to share information about the post study focus groups. The evaluation procedures will be reviewed using an informed script/form (see Post Study Informed Consent Script/Form). Survey completion and focus group participation will be entirely voluntary.

b) Describe solicitation through the use of advertising. (Include plans for using posters, flyers, announcements, newspaper, radio, television or internet ads, face to face interactions, direct mail or phone contact, subject pools, etc.)

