Data will be initially summarized using means, standard deviations, and percentages. Our primary outcome is receipt of HIV testing (tested vs. not-tested) at 12 months. We'll also examine outcomes at 6 months. Churches are the unit of randomization and participants nested in churches will be the level of analysis. Therefore, differences between intervention and standard information groups will be analyzed using random effects logistic regression to account for the clusters and the pairing, or matching, of churches. Multilevel, multivariate models will include fixed-effect terms for experimental condition and potential mediators and moderators, as well as random effect terms for church nested in treatment condition and individual nested within church. This approach has been widely used in other church-based studies. Adjusted odds ratios for HIV testing (and confidence intervals) will be computed for mediators/moderators. Other covariates will be added as indicated by univariate analyses conducted on baseline data. A propensity score matched analysis will also be run using all available covariates. We will use R and SAS statistical software generalized estimating equations and generalized linear mixed modeling for data analyses to determine if there is a difference in HIV screening rates over time between intervention and standard information groups with/without adjusting for covariates. We will do a stratified analysis by Wave to explore differences between: a) Wave 1 intervention and waitlist groups and b) Wave 1 standard information and waitlist groups using similar analysis methods described above. A similar process will also be used to analyze HIV sexual risk behaviors using mixed-model ANOVA programs that allows for adjustment of participant nonindependence within churches.

Specific Aim 2. Evaluate the role of potential mediators and moderators associated with HIV screening behaviors among a church-population at 6 and 12 months.

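### The plan says the TIPS v standard information model accounts for pairing, but its listed terms include neither a pair nor a Wave effect, although arms are randomised within Wave

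*SAP*

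**What the plan says.** Protocol 4a (Research Design) sets the order of allocation: "Matched churches will be randomly assigned to one of two Waves and then to intervention or standard information arms within their Wave". It planned 8 churches in Wave 1 and 6 in Wave 2, with Wave 2 waitlisted for 6 months. Under Data collection, Wave 1 has three surveys (baseline, 6 and 12 months), but "Wave 2 participants will complete the survey four times: baseline 1, baseline 2 (6 months), 12 months, and 18th months".

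Protocol 8a (February 2016 Amendment) records that one intended Wave 1 church withdrew and another was delayed into Wave 2, leaving six in Wave 1. It then says: "Therefore, Wave 2 churches will include 8 churches". The SAP is dated May 2013 and states that it has not been updated since.

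SAP Aim 1, with matching text in Protocol 4i, says the TIPS v standard information contrast uses random effects logistic regression that accounts for both clusters and the pairing of churches. The next sentence lists the terms: "fixed-effect terms for experimental condition and potential mediators and moderators, as well as random effect terms for church nested in treatment condition", and individual within church. Beyond that, "Other covariates will be added as indicated by univariate analyses conducted on baseline data". The SAP uses Wave only in the waitlist contrasts: "We will do a stratified analysis by Wave to explore differences between: a) Wave 1 intervention and waitlist groups", and likewise for standard information.

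**The concern.** Wave is a level at which the trial randomises, and there are three reasons why outcomes could differ by Wave. Calendar period differs by at least the 6-month delay. Wave 2 participants answer a second HIV-testing survey before activities begin. And for some churches Wave was not assigned purely at random: one moved because of other commitments, and Wave 2 churches were still being added in the February, March and August 2016 amendments.

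If neither Wave nor pair is in the model, a Wave difference in testing is counted as unexplained variation between churches. The standard error is then too wide and the test conservative. If arms are also unequal within a Wave, part of the Wave difference enters the estimated TIPS effect.

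The plan can be read two ways. The statement about pairing suggests protection, while the list of terms provides none. An analyst who fits the list and an analyst who follows the statement would fit different models.

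**Working it through.** **Inputs from the documents.** Pilot 12-month rates of 59% v 41%, a difference of 18 points (Protocol 3a), with similar rates expected in this trial (Protocol 4a). More than 65 participants per church at 12 months; 65 is used. 7 v 7 churches. Waves of 6 and 8 churches after the amendment.

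**Assumed.** The Wave shift in testing rate, the between-church SD and the arm split within Wave. The documents give none of these.

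**1. The plan's power figure.** Protocol 4a states "we would have sufficient power with 10 to 12 churches", with 84% for 10 churches and 91% for 12. It uses a coefficient of variation (CV) of cluster rates but does not give its value. The Hayes form, unmatched and two-sided 5%, with c churches per arm, is:

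power = Φ( √[(c−1)(p1−p0)² / V] − 1.96 ), where V = [p0(1−p0) + p1(1−p1)]/m + CV²(p0² + p1²)

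With CV = 0.12, V = 0.4838/65 + 0.0144 × 0.5162 = 0.01488.
- c = 5: √(4 × 0.0324/0.01488) = 2.95, power 83.9%
- c = 6: √(5 × 0.0324/0.01488) = 3.30, power 91.0%
- c = 7: power 95.1%

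The stated figures are consistent with this formula, but the CV was solved from them, so this is not a reproduction from stated inputs. Other variants (matched, one-sided) fit about as well with CV from 0.08 to 0.18. CV 0.12 means a church SD of 0.12 × 41 = 4.9 points to 0.12 × 59 = 7.1 points, so SDs of 5 and 8 points are reasonable trial values.

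**2. Arms balanced within Wave (3:3 and 4:4).** Wave 2 makes up 4/7 of each arm, so the shift cancels and there is no bias. Simulation: 14 churches, 65 per church, least squares on church proportions, 40,000 runs per cell, 18-point effect.

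| Between-church variation | Wave shift | Power, condition only | Power, with Wave |
|---|---|---|---|
| SD 5 | 5 points | 96.5% | 97% |
| SD 5 | 10 points | about 94% | 97% |
| SD 8 | 5 points | 85% | 86% |
| SD 8 | 10 points | 80% | 86% |
| CV 0.12 | 10 points | 89% | 94% |
| CV 0.12 | 15 points | 81% | 94% |

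With a 10-point shift, type I error without Wave is 2.1% (SD 5) or 2.9% (SD 8). At CV 0.12 it is 2.0%, falling to 0.7% for a 15-point shift. With Wave in the model it is about 5% throughout.

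**3. A pair effect, pairs intact within Wave.** At CV 0.12, type I error is 5% and power 90% at every shift, so Wave drops out without its own term. The 90% is below 94% because fixed pair effects leave 14 − 8 = 6 degrees of freedom, against 14 − 3 = 11 for condition plus Wave, and the simulation gives matching no gain in similarity.

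**4. Arms unequal within Wave, two pairs split.** Illustration: 2 TIPS and 4 standard churches in Wave 1, 5 and 3 in Wave 2. Bias = shift × (5/7 − 3/7) = 2/7 × shift.
- 5-point shift: 1.4 points
- 10-point shift: 2.9 points
- 15-point shift: 4.3 points

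The sign reverses if the split is reversed. Simulation gives the same bias with condition only and with condition plus pair. With a pair term the rejection rate under no effect is 5.6%, 7.0% and 7.9%. With a Wave term the bias is zero.

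**The case against.** The strongest reply is that the plan already covers this. It says pairing is accounted for. Protocol 4a calls the trial a matched-pair design and sends matched churches to a Wave before arms are assigned, so by design each pair lies inside one Wave, and a pair effect would remove Wave differences (step 3). This stands for the design as intended. It does not close the gap, because the list of terms contains no pair effect, and because one church left and another changed Wave. If the eight intended Wave 1 churches formed four pairs and the two losses were unrelated to pairing (both assumptions), the losses fell in different pairs in 24 of 28 combinations. The documents do not say how the pairs were rebuilt.

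A reader might infer that arms did become unequal within Wave and that the estimate is therefore biased. The documents do not support this. Waves of 6 and 8 are compatible with 3:3 and 4:4, Wave 2 recruitment was still open, and it is not stated whether arms had been assigned when the changes occurred.

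A reader might also infer a large loss of power. With a 10-point effect, SD 5 and a 10-point shift, power would fall from 58% to 43%. But the documented planning difference is 18 points, and there the losses are those in step 2.

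It can also be said that Wave is known before activities start and could enter through the baseline covariate screen. It could, but the screen is data-driven and does not guarantee it. Nor can baseline data show differences that arise later from calendar period or the extra survey.

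**Conclusion.** The point holds as a gap in specification. The plan promises to account for pairing, lists no pair term and no Wave term, and predates the change in Wave membership. It would be too strong to say that Wave differences necessarily go into the error or the effect: a pair effect with intact pairs would prevent both.

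Under the listed terms with balanced arms, the consequence is a conservative test. The loss is about 1 point of power for a 5-point Wave shift, and about 3 to 6 points for a 10-point shift. Bias arises only if arms are unequal within Wave, and in that case a pair effect alone does not remove it.

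These sizes rest on an assumed Wave shift, an assumed SD (or the back-solved CV), 65 completers per church, and a church-level linear approximation to the planned logistic model. The missing terms are certain; the size of the harm is not known.

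**What to change.** In SAP Aim 1 and Protocol 4i:
- Prespecify Wave, as actually conducted, as a fixed effect in the TIPS v standard information model, whatever the baseline screen shows. Add Wave-by-time in the over-time analysis.
- If a pair effect is kept, name it as a term and say how pairs affected by the February 2016 changes are handled. Wave is redundant if pair effects are fixed and all pairs are intact.
- State the number of TIPS and standard information churches in each Wave.
- Define which Wave 2 surveys count as baseline, 6 and 12 months. Wave 2 has two baselines and then surveys labelled 12 and 18 months, and a Wave term cannot settle which is the primary time point.

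No new data are needed. In the unpaired model the cost is one church-level degree of freedom (12 to 11). If Wave has no effect, this loses under 1 point of power with balanced arms, and about 1 to 5 points if arms are unequal within Wave.

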Church-based HIV/STD testing. The Kansas City Health Department will provide three free HIV/STD testing events at both the intervention and standard information control arm participating churches, as part of their usual church-based HIV/STD screening, using their standard community-based standard procedures. Church health liaisons will coordinate the screening events for their churches. Free HIV/STD testing is also provided at KCHD clinics and community clinics (e.g., KC CARE); church and community members who do not want to get tested in church can receive free HIV/STD testing at these location if they so chose. KCHD will follow-up with clients with their screening results as needed following their standard protocols. KCHD will report total number of persons tested/receiving results with aggregate, de-identified demographics (e.g., age, gender), and number of HIV+ tests given per church to study staff. Individual participants' results will not be shared with church leaders/members or study staff since KC Health Department will not be provided any information about study participants; therefore, they will not know whether persons voluntarily seeking HIV/STD testing are involved in this study. KC CARE Clinic's HIV Linkage to Care free services, following their standard community-based procedures, will also be available

Protocol Title: Assessing an HIV Education and Screening Intervention in African American Churches

Protocol Type: Expedited/Full Board Application

Date Submitted: 11/21/2017

Approval Period: 12/05/2017-12/04/2018

Important Note: This Print View may not reflect all comments and contingencies for approval. Please check the comments section of the online protocol. Questions that appear to not have been answered may not have been required for this submission. Please see the system application for more details.

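### For the over-time comparison the SAP lists only church and individual random effects, so the arm-by-time test exceeds 5% if churches' testing rates change by different amounts

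*SAP*

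**What the plan says.** SAP, Specific Aim 1, makes three statements that bear on this point.

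- The endpoint: "Our primary outcome is receipt of HIV testing (tested vs. not-tested) at 12 months". Arm differences are to be analysed by random effects logistic regression that accounts for the clusters and the matching of churches.
- The model terms: "fixed-effect terms for experimental condition and potential mediators and moderators", together with "random effect terms for church nested in treatment condition and individual nested within church". Protocol section 4i repeats this list.
- The over-time comparison: GEE and generalised linear mixed models, in R and SAS, "to determine if there is a difference in HIV screening rates over time between intervention and standard information groups", with and without covariates.

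Neither document mentions a church-by-time random effect, a church-specific slope, a covariance structure, the cluster level for GEE, or a degrees-of-freedom or small-sample rule. An arm-by-time term is not written out either, but it is the natural reading of a between-arm difference in rates over time.

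The over-time comparison is not incidental. The power analysis in Protocol section 4a is based on "change in expected self-reported HIV testing rates (primary outcome) from baseline to 12-month assessment", with a 5% type I error rate.

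**The concern.** A random effect for church absorbs a church's constant level. It does not absorb one church's testing rate rising more than another's between surveys. A random effect for the individual is also constant over time. With only these two terms, church-level differences in change are treated as if they were independent person-level noise. The arm-by-time contrast then uses hundreds of participants as its effective sample instead of 14 churches with 12 degrees of freedom.

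Uneven change is plausible here. Protocol section 4a admits churches that have not hosted an HIV-related event in the last year, then provides "three free HIV/STD testing events at both the intervention and standard information control arm participating churches", coordinated by each church's own liaisons. How well those events are attended can differ from church to church. That is an inference from the design; the documents give no figure for it.

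At stake is the interval for the change attributable to the intervention, which would be too narrow, and a positive over-time result, which could not be claimed at 5%.

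**Working it through.** **Inputs from the documents.** Protocol section 4a gives 14 churches, 7 per arm; 110 participants per church at baseline and more than 65 at 12 months; and power of 84% with 10 churches and 91% with 12. Protocol section 3 gives the pilot rates: 22% to 59% (intervention) and 19% to 41% (comparison).

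**Assumptions.** A two-sided test; the coefficient of variation (CV) k, which the protocol uses but does not print; and the correlation ρ between a church's baseline and 12-month levels.

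**1. Recover the CV from the stated power.** With c churches per arm, m = 65, p0 = 0.41 and p1 = 0.59:

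V = [p0(1−p0) + p1(1−p1)]/m + k²(p0² + p1²) = 0.4838/65 + 0.5162k²

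power = Φ(√[(c − a)(p1 − p0)²/V] − 1.96), with a = 1 (unmatched) or a = 2 (matched).

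- Unmatched, k = 0.12: V = 0.00744 + 0.00743 = 0.01488. For c = 5, √(4 × 0.0324/0.01488) = 2.95, giving 84%. For c = 6, √(5 × 0.0324/0.01488) = 3.30, giving 91%.
- Matched, k = 0.085: V = 0.00744 + 0.00373 = 0.01117. For c = 5, √(3 × 0.0324/0.01117) = 2.95, giving 84%. For c = 6, √(4 × 0.0324/0.01117) = 3.41, giving 93%.
- Matched, k = 0.12: 72% and 84%.

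The unmatched formula fits both stated powers, but the design is matched. I therefore carry 0.085 to 0.12 as a range.

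**2. Confirm that church drops out.** In a linear version with church and person intercepts, the arm-by-time standard error was 0.06937. A two-sample test on individual changes that ignores church gave the same 0.06937.

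**3. Size by hand.** A CV of k at rate p is a logit SD of about s = k/(1 − p). At p = 0.41 this is 0.144 for k = 0.085 and 0.203 for k = 0.12. The church-by-time variance at each survey is (1 − ρ)s². Then

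DE = 1 + m(1 − ρ)s²p(1 − p), and false-positive rate = 2[1 − Φ(1.96/√DE)].

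| k | ρ | (1 − ρ)s² | DE | Rate |
|---|---|---|---|---|
| 0.085 | 0.8 | 0.0042 | 1.07 | 5.8% |
| 0.085 | 0.5 | 0.0104 | 1.16 | 6.9% |
| 0.085 | 0 | 0.0208 | 1.33 | 8.9% |
| 0.12 | 0.8 | 0.0083 | 1.13 | 6.5% |
| 0.12 | 0.5 | 0.0207 | 1.33 | 8.9% |
| 0.12 | 0 | 0.0414 | 1.65 | 12.7% |

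This approximation uses one rate for both surveys and runs high, as step 5 shows.

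**4. Simulated null, 65 per church, individual changes treated as independent.** For ρ from 0.5 to 0, rejection was about 7–8% at k = 0.085 and 7–10% at k = 0.12. At ρ = 0.8 it was about 6–6.5%, and at ρ = 1 near nominal. A church-level test of change stayed near 5%.

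**5. Simulated null, logistic mixed model with the listed terms.** The set-up was 14 churches, 110 at baseline and 65 at 12 months, church SD 0.3 and person SD 1.0 (logit), 3,000 trials per setting, and a likelihood-ratio test of arm-by-time.

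| Church-by-time SD (logit) | Listed model | Step 3 formula (p = 0.40) |
|---|---|---|
| 0 | 4.8% | 5.0% |
| 0.1 | 6.1% | 6.8% |
| 0.2 | 11.4% | 12.4% |
| 0.3 | 17.8% | 20.6% |
| 0.4 | 25.6% | 29.5% |

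At SD 0.2, person SDs of 0.5 and 1.5 gave 12.2% and 10.2%. The back-solved CVs reach at most about 0.20 on this scale, so the last two rows only show the trend.

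**6. Alternatives under the same null.** Over all settings, a t test on church-level change (12 df) rejected 4.7–5.4%. GEE clustered on church, with an uncorrected sandwich variance and a normal reference, rejected 8.8–10.3%. A church-level t test at 12 months alone rejected 4.5–5.3%.

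**The case against.** The best defence is that the SAP never specifies this faulty model outright. The random-effects list belongs to the sentence on condition, mediators and moderators. The over-time sentence comes later and lists no terms. The list also looks incomplete, because matching is to be accounted for and yet no pair term appears. Part of this stands: the over-time model is under-specified. But an individual random effect cannot be separated from residual variation with one binary answer per person, so the list describes a repeated-survey model, and it is the only one given. A pair intercept would not help, because it also cancels from change.

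Second, GEE is named alongside the mixed model. Clustered on church, it would absorb uneven church change. That is correct. A reader might infer that GEE will be clustered on the participant, but neither document says so. Church clustering alone is not sufficient, however: with 14 churches and no correction it still rejects about 9–10%.

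Third, the size depends on inputs that the documents do not give. This stands in full. Both arms receive three testing events from one provider under standard procedures, and change could be close to parallel.

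Finally, a reader might infer that the primary analysis fails. The documents do not support that. The stated endpoint is at 12 months, where a church random effect carries all church-level variation.

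**Conclusion.** The point holds for the over-time comparison only. If the listed random effects are used as written and churches change by different amounts, the arm-by-time test ignores the randomised unit and rejects a true null more than 5% of the time.

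For CVs of 0.085 (matched formula) to 0.12 (unmatched), the rate is about 7–10% at church correlations of 0.5 to 0 and about 6–6.5% at 0.8. There is no inflation if churches change in parallel on the model's scale. The upper end is soft by a few points: at CV 0.12 and zero correlation, the pooled-change simulation gives about 10%, the fitted mixed model about 11% and the hand formula about 13%. Rates near 20% would need church-by-time variation larger than the stated power implies, and nothing in the documents supports that.

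The direction is certain given uneven change; the amount is not. It would be wrong to conclude that the 12-month primary comparison is compromised. The over-time result still matters, because the protocol's power analysis is based on change.

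**What to change.** Amend SAP, Specific Aim 1, for the over-time analysis:

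- Write out the arm-by-time term, add a random church-by-time effect, and test arm-by-time on church-level degrees of freedom.
- Alternatively, analyse church-level changes from baseline with a t test: 14 − 2 = 12 df unmatched, or 7 − 1 = 6 df if paired.
- If GEE is used, state church as the cluster and use a small-sample-corrected variance with a t reference.

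Only the church-level change test was shown here to hold about 5%. The enlarged logistic mixed model was not fitted, so its behaviour with 14 churches should be checked by simulation, or the church-level test named as the reference analysis.

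The change takes a short SAP addition and no new data. If churches change by different amounts, intervals for the over-time effect widen and power for that test falls somewhat. The 12-month comparison needs no change on this account.
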